Any human subjects research that is not being conducted in compliance with applicable institutional policy and Good Clinical Practices will be suspended by the IRB. An IRB shall have authority to suspend or terminate approval of research that is not being conducted in accordance with the IRB's requirements or that has been associated with unexpected serious harm to subjects. Any suspension or termination of approval shall include the necessary and appropriate notifications of such actions to the institution's administration, funding agency, ACS other sponsor.

DATA QUALITY AND INTEGRITY

Because of the ongoing monitoring of the project, study investigators and staff are responsible for ensuring that data quality assurance procedures are developed and maintained. Several procedures will be used to maintain the integrity of the data. All databases will be stored in a centralized location on one of the departmental servers, which is backed up daily, with access limited to specific users at the discretion of the PI. The PI will assure that audits of selected subsets of data are performed and that appropriate safeguards of participant privacy are maintained. Privacy safeguards will include appropriate password protection and physical security for all computer systems. Patient names will not be stored in data files; records linking participants' names with the computer identifiers will be kept in a separate file and encrypted.

A relational database will be created in Microsoft ACCESS to store all project-related data. ACCESS can accommodate complex relationships among tables, allowing large quantities of data to be integrated into a single database. Relational databases such as ACCESS also allow for powerful and flexible queries and reports. ACCESS can be easily customized using Visual Basic for Applications (VBA) code, allowing the inclusion of many design features ideal for behavioral science research. These features include more user-friendly interfaces, the ability to specify valid ranges for variables, and double-entry systems for data, all of which help to maintain data integrity. We will use the built-in security features of ACCESS to restrict user access.

Additional quality assurance procedures include a data collection protocol documented in a protocol manual; a two-stage editing procedure for survey data collection consisting of the initial review of the data collection form by a project member immediately following data collection, and a second review by a project member who will record any significant deviations from the protocol; and regular meetings between the study statistician, the PI, data managers, and other project staff to review problems and solutions, and discuss concerns. Data entry systems, whether via scannable forms, or hand entry with verification, specifically provide field checks, range checks for continuous variables and valid value checks for categorical variables; checks for legitimate dates and times and logical consistency. A specific audit trail system that identifies the date, time, and individual making changes on the database will be part of the data-entry system. During data collection, we will either issue reports weekly or following any new data entry, depending on the needs of the project. Queries and reports will be provided to the study statistician and the PI.

F. Relevance to the cancer problem

Approximately 50% of patients diagnosed with cancer die of progressive disease. The overwhelming majority of patients develop devastating physical and psychosocial symptoms. Those symptoms decrease the quality of life of patients. Circulating cytokines and inflammatory proteins have been thought to be directly associated with pain, and cognitive impairment, depression, fatigue, cachexia, and sleep disorder. Steroids decreases the intensity of symptoms namely Fatigue, nausea, anorexia and pain that occur frequently in advanced cancer and one of the mechanisms it exerts such effects by decreasing a cytokines levels that mediate these symptoms. Despite widespread acceptance and frequency of steroid therapy in patients with cancer symptom management, the data is inadequate to draw definitive conclusions about the efficacy of these compounds in the management of pain and other symptoms. The role steroids on cancer related fatigue, pain, appetite and nausea (which are common symptoms in advanced cancer), their effects on cytokines need to be defined through

2005-0816 April 5, 2011 Page 49 of 60

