We **hypothesize** that dexamethasone decreases the intensity of symptoms namely Fatigue, nausea, anorexia and pain that occur frequently in advanced cancer and one of the mechanisms it exerts such effects by decreasing a cytokines levels (namely IL-1, IL-6, TNF- α , IL-10, IL-8, activated monocytes and corresponding receptor levels) and C-reactive protein that mediate these symptoms.

Specific aim #4: To collect pilot data on the quality of sleep and cortisol levels in ten subjects.

Measure of sleep quality: The Pittsburg Sleep Quality Index (PSQI) will be used to measure subjects' sleep quality. The PSQI (Appendix N) is a 9-question, 19 item self-report instrument designed to measure sleep quality. PSQI questions 1-4 request specific respondent information that is filled in by hand, such as customary bed time and length of time to fall asleep. PSQI questions 5-8 are answered on a 0-3 scale with 0

indicating no symptom presence and 3 representing symptom presence 3 or more times the past week. Question 9 is answered on a 0-3 scale with 0 meaning "very good" and 3 representing "very bad." All scores are combined according to the scoring criteria included with the form to produce a Global PSQI Score. Scores above 5 indicate clinically meaningfully disturbed or poor sleep.

Cronbach's alpha coefficient produced an average internal consistency reliability estimate of .80 for the Global PSQI Score across numerous patient populations with a variety of different physical ailments. Additionally, the PSQI is more highly correlated with sleep problems (r = .69-.77) than with unrelated constructs, such as mood symptoms and depression (r = .22-.65). Additionally, Global PSQI Scores above 5 resulted in a sensitivity of 98.7 and specificity of 84.4 to persons with sleep disturbances versus controls. (http://www.bmedreport.com/archives/6559)

Salivary cortisol levels were assessed by enzyme immunoassay (Salimetrics, State College, PA http://www.salimetrics.com/products

and services/salivary assays/specifications/cortisol.php). This assay has a lower detection limit of less than 0.003/dL. The mean intraassay coefficient was 5.5 (range, 4–6%) and the mean interassay coefficient was 8.2 (range, 7–11%). All samples from a participant were analyzed in duplicate in the same assay to minimize variability. Appendix O explains the testing protocol.

Cytokine Measures

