Fifty evaluable patients per group will also allow us to detect a difference between groups for other symptom variables (of pain, anorexia and nausea) of approximately one-half a standard deviation (assuming a one-sided significance level of 0.05 and 80% power), or approximately 0.57 standard deviations for two-sided tests. Analyses will be made as above for fatigue. The variable pain will be assessed using the BPI, anorexia will be assessed using the FAACT, and nausea will be assessed using the ESAS.

Given that we will also have measurements available at 8 days (in addition to baseline and two weeks later), we will also conduct a repeated measures analysis of variance on each of the symptom variables. These analyses will include main effects of group and time (with three time points) and an interaction term of group by time. In addition, information will be graphically summarized by group for all days, including days 22 and 29, when dexamethasone will be provided open label.

The third objective will determine if there is more of a change over time in cytokines for the group that receives dexamethasone as compared to the placebo group. Analyses will be similar to those made for the symptom variables. We will initially analyze difference scores between baseline and two weeks later by use of a t test if the data are approximately normally distributed and by a Wilcoxon test if not. We will also conduct analyses using a repeated measures analysis of variance with time points of baseline, 8 days and two weeks later. As above these analysis will include main effects of group, time, and a group by time interaction.

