The associations between symptom and cytokine change scores at two weeks from baseline will also be explored. We will determine the correlations between all combinations of the symptoms of fatigue, pain, anorexia and nausea, the cytokines IL1, IL6, TNF- α , IL-10, IL-8, activated monocytes and corresponding receptor levels, and C-reactive protein. If the data are approximately normally distributed we will use a Pearson's correlation coefficient to measure these associations, and otherwise will use a Spearman's correlation coefficient. If necessary, we will transform the data to achieve approximately normal distributions. Our initial hypothesis is that when symptoms increase in severity, cytokine levels also increase. We will be able to declare correlation coefficients greater than 0.39 as statistically significant with a two-sided significance level of 0.05 and 80% power.

We will also investigate how cytokines and C-reactive protein are related in combination to the symptoms of fatigue, pain, anorexia, and nausea. These analyses will be made separately for each symptom. We will use a repeated measures analysis with the change in symptom score between baseline and two weeks as the dependent variable, with the cytokines (IL1, IL6, TNF- α , IL-10, IL-8, activated monocytes and corresponding receptor levels) and C-reactive protein as independent variables, over three time points. Differences overall between groups will also be tested by this model, in addition to a test of a time effect and a group by time interaction effect.

Summary information on the global symptom evaluation by group will also be provided at each of the assessed time points. Differences in distributions between groups will be analyzed using a chi-square analysis.

When a total of 50 patients (one-half of total number of evaluable patients) have been entered and evaluated, the statistical collaborator will conduct an interim monitoring of efficacy and toxicity. Results will be presented overall and by arm retaining the blinding as to arm assignment. The PI and other collaborators (other than the statistical collaborator) will remain blinded as to the arm assignments of patients. We plan to stop

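### The combined marker–symptom model tests group differences while adjusting for post-randomisation cytokines and CRP, so its group terms are not treatment effects; the efficacy comparisons are unaffected

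*Combined protocol and SAP*

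**What the plan says.** The combined model is described twice in the Combined protocol and SAP, in the same terms: in the outcome-measures section under the specific aim on association of cytokines with symptoms, and under Statistical Considerations.

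- Outcome, one model per symptom: "We will use a repeated measures analysis with the change in symptom score between baseline and two weeks as the dependent variable".
- Covariates: the cytokines, receptor levels and activated monocytes, "and C-reactive protein as independent variables, over three time points".
- Treatment test: "Differences overall between groups will also be tested by this model". Time and group-by-time tests are also named.

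The model's description does not list its three time points. The cytokine analysis of variance in Statistical Considerations does: "time points of baseline, 8 days and two weeks later". I take the same three to apply here.

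The plan puts the markers on the path from drug to symptom:

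- Mechanism (specific aim #3, also section 10.2 and B. Specific Aims): "one of the mechanisms it exerts such effects by decreasing a cytokines levels".
- Drug to marker: the third objective is to "determine if there is more of a change over time in cytokines for the group that receives dexamethasone".
- Marker with symptom: "Our initial hypothesis is that when symptoms increase in severity, cytokine levels also increase".

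The model is not called a mediation or direct-effect analysis, and nothing says how its group test is to be read.

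**The concern.** A treatment comparison is protected by randomisation only if it does not condition on what happens afterwards. Here the group term is adjusted for markers measured at day 8 and day 15, and the plan expects dexamethasone to move those markers and the markers to move with symptoms.

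Two things follow. First, any benefit that runs through the measured markers is taken out of the group term. Secondly, if marker and symptom have common causes such as disease progression or infection, conditioning on the marker makes the arms unlike each other in those causes. The remaining coefficient is then not a clean estimate of the unmediated part either.

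The plan would thus give two kinds of group test for each of four symptoms (fatigue, pain, anorexia, nausea), both described as group, time and group-by-time, with different meanings and no label to tell them apart. A small or null marker-adjusted difference could be read as lack of efficacy when it is what mediation would produce.

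**Working it through.** **Inputs from the plan (Statistical Considerations).** Total effect ½ SD, about 7 FACIT-F points; SD of change 13.95; 50 evaluable per arm; one-sided 0.05; 80% power.

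**Plan's own figure.** n per arm = 2(1.645 + 0.842)²/0.5² = 49.5, so 50. Power with 50 per arm: the SE of the difference is √(2/50) = 0.200 SD, 0.5/0.200 = 2.5, and Φ(2.5 − 1.645) = 0.80. The figure reproduces. The plan gives no figure for the combined marker model.

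**Assumptions (not in the documents).** One composite marker, within-arm SD 1, coded so that improvement is positive. Treatment shifts it by *a* SD, and a share *p* of the total effect T = 0.5 SD passes through it. Within-arm SD of symptom change is 1, and 1 SD is taken as 7/0.5 = 14 points.

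**Formulae.**
- Marker slope: b = pT/a
- Marker-adjusted group difference: d = T(1 − p)
- Variance inflation from correlation between group and marker (1:1 allocation): 1 + a²/4
- SE(d) = √[(1 − b²)(2/50)(1 + a²/4)]
- One-sided power = Φ(d/SE − 1.645)

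**Half mediated (p = 0.5): d = 0.25 SD = 3.5 points.**

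| a | b | 1 − b² | 1 + a²/4 | SE | d/SE | one-sided power |
|---|---|---|---|---|---|---|
| 0.5 | 0.500 | 0.750 | 1.063 | 0.179 | 1.40 | 0.40 |
| 0.8 | 0.313 | 0.902 | 1.160 | 0.205 | 1.22 | 0.34 |
| 1.0 | 0.250 | 0.938 | 1.250 | 0.217 | 1.15 | 0.31 |

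The plan does not state the sidedness of this test. With 1.96 in place of 1.645, power is 0.29, 0.23 and 0.21, against Φ(2.5 − 1.96) = 0.71 unadjusted.

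**Other shares, a = 0.8 (one-sided).** 0%: 7.0 points, power 0.75. 25%: 5.25 points, 0.55. 75%: 1.75 points, 0.16. 100%: 0 points, 0.05. Even with no mediation some power is lost to collinearity.

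**Simulation (50 per arm, 4,000 runs, a = 0.8, p = 0.5).** Adjusted difference 0.25 SD, rejection 0.33; unadjusted 0.50 SD, rejection 0.80. Adding 11 unrelated marker covariates leaves the estimate at 0.25 SD and lowers rejection to 0.30.

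**Shared cause of marker and symptom (assumed loading 0.5 on each, a = 0.8).** The slope picks up 0.5 × 0.5 × √(1 − b²), and the group term loses *a* times that.
- p = 0: 0.50 − 0.8 × 0.25 = 0.30 SD (simulated 0.29), although nothing is mediated.
- p = 0.5: 0.25 − 0.8 × 0.25 × 0.950 = 0.06 SD (simulated 0.06).
- p = 1: 0 − 0.8 × 0.25 × 0.781 = −0.16 SD (simulated −0.16), a reversed sign.

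**The case against.** The strongest reply is that efficacy is already tested without markers. Fatigue change is compared by t test or Wilcoxon test; pain, anorexia and nausea are handled the same way; the repeated measures analysis of each symptom contains only group, time and their interaction; and the interim rule uses the group difference in fatigue reduction with no mention of markers. The combined model belongs to the association objective, and its group test is described as an additional one. All of this stands, and it limits the consequence to a secondary analysis.

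The size is also driven by assumption. The adjusted estimate is simply 7 × (1 − share), and the sketch uses one composite marker at one time point, not the planned multi-marker model. That stands too: the direction under mediation is secure, the magnitude is illustrative.

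Three stronger inferences are tempting but unsupported:

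- A reader might infer that the adjusted difference should vanish if the trial's hypothesis is true. The plan calls cytokine reduction only one mechanism. Its section on corticosteroids and symptoms lists others, including tumour mass, peritumoral oedema and central effects, and the cytokine section allows that local production may matter when circulating levels are not raised.
- A reader might infer that the more dexamethasone works through cytokines, the smaller this group difference must be. That holds only for a fixed total effect. With a direct effect fixed at 0.25 SD, the adjusted term stays at 0.25 SD however large the indirect part; only its shortfall from the total grows.
- A reader might infer that group should be dropped from the model. Treatment may move both markers and symptoms, so omitting group could confound the pooled marker–symptom association, which is the model's purpose.

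**Conclusion.** The point holds for the combined marker–symptom model. As written, the plan tests group differences there conditional on markers that it places on one causal pathway. The group and group-by-time terms are not treatment effects. At best they describe the part not passing through the measured markers, and shared causes can bias them even for that.

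For a fixed total effect of 7 points, with half assumed mediated and an assumed marker shift of 0.5 to 1 SD, the expected difference is 3.5 points with one-sided power of about 0.31 to 0.40, against 0.80 unadjusted. The timing of the markers is inferred from the neighbouring cytokine analysis.

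A reader might go further and infer that the trial's efficacy conclusion is at risk, or that a null result here would contradict the primary test. The documents do not support that: the primary, secondary symptom and interim comparisons are free of markers, and shrinkage after marker adjustment is compatible with a real overall effect. This is a moderate fault in a secondary analysis.

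It is separate from another weakness of the same model: a single baseline-to-two-week change per patient supplies no repeated outcome from which to estimate time effects. If change at each visit were used instead, the day 8 and day 15 markers would still be post-randomisation and this point would remain.

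**What to change.** In both places where the model is described, remove the statement that it tests differences between groups. State that all treatment effects, including group-by-time, come from the marker-free t test or Wilcoxon comparisons and the marker-free repeated measures analyses in Statistical Considerations. Name the three time points at which the markers enter the model.

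Keep the markers, which the association objective needs. Group may stay as an adjustment term. If its coefficient is reported, show it beside the unadjusted total effect for the same symptom, label it as marker-adjusted (the part not passing through the measured markers, assuming no shared causes), and say that it is not used to judge efficacy.

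The cost is a few sentences of analysis-plan wording. No new data, assessments or patients are needed.

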The reason to have open label design after Day15 is to observe the descriptive trends. Exam (including history including FACIT-F, FAACT, HADS, ESAS, BPI, GSE (on days 8, 22, and 29), physical exam and toxicity assessment will be done day 0(baseline), Day 8 [± 3 days], Day 15 [± 3 days], Day 22 [± 3 days] Day 29 [± 3 days]. ESAS and Toxicity will be done on day 4. A physician will do a physical exam on the patient on day 0, 15, and Day 29; and the nurse will do a nursing assessment on days 8, and day 22. If patient is unable to return to clinic on Day 8, 15, 22, or 29 the assessments will be done by the research nurse by phone. Laboratory correlates including cytokine levels- IL-1, IL-6, TNF- α , IL-10, IL-8, activated monocytes and corresponding receptor levels, C-reactive protein, complete blood counts, chemistry (electrolytes) within 7 days of baseline, Day 8 [\pm 3 days], Day 15 [± 3 days], Day 22 [± 3 days], and Day 29 [± 3 days]. If patients are unable to return to clinic on Day 8, 15, 22, or 29 the laboratory correlates will not be done. Patients will also be assessed by the research nurses for any signs and symptoms of infection while on the study drug. All study patients will be asked to return to the clinic for follow-up assessments 2 weeks after the study medication is discontinued (day 43 ± 3 days) for a safety and toxicity assessment. If the patient is unable to return to the clinic on day 43, the safety and toxicity assessment will be done by the research nurse by telephone.

The electrolytes measured will include chloride (Cl), carbon dioxide (CO2), Potassium (K) and Sodium (Na).

Treatment plan is illustrated in Figure 2.

Figure 2.

2005-0816 April 5, 2011

| | | | - | | | | Page 30 of 60 |
|----------------|----------|-----|-------|-------|-------|-------------|---------------|
| Assessments | Baseline | Day | Day 8 | Day | Day | Day 29 | Dăy 43 [± 3 |
| | | 4+ | [± 3 | 15[± | 22 | [± 3 days] | days] |
| | | | days | 3 | [±3 | | |
| | | | | davs] | days] | | |
| MDAS | Х | | | | | | |
| | | | | | | | |
| BPI | Х | | Х | Х | Х | Х | |
| FACIT-F | Х | | Х | Х | Х | Х | |
| FAACT | Х | | Х | Х | Х | Х | |
| HADS | Х | | Х | Х | Х | Х | |
| r-ESAS | Х | Y | Х | Х | Х | Х | PE or Y |
| GSE | | | Х | | Х | Х | |
| Toxicity | Х | Y | Х | Х | Х | Х | PE or Y |
| Demographics | Х | | | | | | |
| Cytokine, | Within 7 | | Х | Х | Х | Х | |
| Activated | days | | | | | | |
| monocytes | - | | | | | | |
| and | | | | | | | |

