- Symptom Measure (Depression): Hospital Anxiety and Depression Scale (HADS): This 14 item questionnaire has been validated in a number of clinical situations and has been widely used in medically ill patients [129], Although its use in cancer patients has been somewhat limited, we believe its proven validity in the clinical setting makes it well-suited for our study.
- **Global Symptom Evaluation.** This instrument is to estimate the minimal important difference in symptoms before treatment and after treatment. Patients will be asked about their symptoms (worse, about the same, or better) after starting new medication. If their answer is better, patients will be asked to rate how much better their symptoms are (almost the same, hardly any better at all, a little better, somewhat better, moderately better, a good deal better, a great deal better, a very great deal better). If their answer is worse, patients will be asked to rate how much worse their symptoms are (almost the same, hardly worse at all, a

little worse, somewhat worse, moderately worse, a good deal worse, a great deal worse, a very great deal worse) [130,131].

- **Toxicity Assessment**: The potential side effects of Dexamethasone will be assessed using the side effects recording sheet based on NCI common toxicity criteria.
- **Demographic variables.** The variables of age, gender, education, race, and ethnicity, cancer diagnosis will be assessed at baseline.

STATISTICAL CONSIDERATIONS

Prior to inferential procedures, extensive descriptive statistical analyses of the outcome and predictor variables will be conducted. Standard descriptive statistics including means, standard deviations, ranges, and frequencies, together with 95% confidence intervals, will be computed where appropriate. Distributional characteristics of relevant variables will also be more closely examined using boxplots and histograms. If the data do not appear to be approximately normally distributed, transformations will be made to the data. Bivariate associations will be explored using Pearson's Product Moment correlation coefficients, scatterplots, and contingency tables.

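### The Global Symptom Evaluation is an ordered scale, but the arms are compared with a chi-square test that ignores the order (minor)

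*Combined protocol and SAP*

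**What the plan says.** The GSE is described under Other Assessments as a two-step rating. First: "Patients will be asked about their symptoms (worse, about the same, or better) after starting new medication". A patient who answers better then picks a grade: "almost the same, hardly any better at all, a little better, somewhat better, moderately better, a good deal better, a great deal better", followed by one still higher grade. A patient who answers worse picks from a mirrored list that ends "little worse, somewhat worse, moderately worse, a good deal worse, a great deal worse, a very great deal worse".

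Statistical Considerations promises a summary of the GSE by group at each assessed time point and then adds: "Differences in distributions between groups will be analyzed using a chi-square analysis". It gives no number of categories, collapsing rule, sidedness, effect estimate or power for the GSE.

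The schedule in section E (Research design and Methods) places the instrument at "GSE (on days 8, 22, and 29"; the assessment table agrees. Day 15, the time of the primary comparison, is not among these days. Statistical Considerations refers to "days 22 and 29, when dexamethasone will be provided open label", and section 10.4 (Study Design) puts all patients on open-label drug from day 15.

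**The concern.** The instrument is built so that each answer ranks above or below the next. A Pearson chi-square test treats the answers as unordered labels: shuffle the columns and the statistic does not change. It spreads its sensitivity over every possible difference in distribution, when the question here is whether one arm reports more improvement. If many levels are tabulated, the cells are also sparse.

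The choice stands apart from the rest of the plan. Fatigue, pain, anorexia, nausea and the cytokine changes all have the Wilcoxon test as the fallback, and the correlations fall back on Spearman. No reason is given for treating the GSE differently.

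What is at stake is the chance of seeing a real shift in patients' own rating of change at day 8, the one GSE assessment made while one arm is on placebo.

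**Working it through.** **Inputs from the documents.** 50 evaluable patients per arm; primary effect of 0.5 SD (about 7 FACIT-F points); SD of change 13.95; one-sided 0.05 and 80% power; 0.57 SD for two-sided tests on other symptoms; up to 80 per arm entered to allow for 37% dropout (Statistical Considerations and Missing Data).

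**The plan's own figures reproduce.**
- One-sided, 0.5 SD: n = 2(1.645 + 0.842)²/0.5² = 49.5, so 50 per arm. Using 7/13.95 also gives 50.
- Two-sided, 0.57 SD: n = 2(1.960 + 0.842)²/0.57² = 48.3, so 49 per arm, consistent with 50.
- Dropout: 100/(1 − 0.37) = 159, against 160 stated.

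None of these concerns the GSE, for which the plan states no effect size.

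**Number of levels.** Counting the response list: 8 better + 1 same + 8 worse = 17. The plan never states this number. The first step alone has 3 categories.

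**Sparsity.** 50/17 ≈ 2.9 expected per cell if the 17 levels were equally likely.

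**Assumptions for power.** A normal latent response shifted by 0.5 SD (borrowed from the day-15 FACIT-F calculation) and cut into ordered categories. For 17 levels the shapes were equal probability, equal width, and an uneven 25/30/45 split of worse/same/better. For 3 levels they were equal thirds, 25/30/45 and 20/30/50. Both tests are two-sided at 0.05, the rank-sum test is tie-corrected, and there were 20,000 simulated trials per setting.

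| Categories tabulated | Per arm | Shift | Chi-square power | Rank-sum power, same categories |
|---|---|---|---|---|
| 17 | 50 | 0.5 SD | 16–19% | 67–68% |
| 17 | 50 | 0.57 SD | 21–26% | 78–79% |
| 17 | 80 | 0.5 SD | 33–37% | 86% |
| 3 | 50 | 0.5 SD | 44–49% | 54–59% |
| 3 | 50 | 0.57 SD | 55–60% | 65–70% |
| 3 | 80 | 0.5 SD | 65–70% | 75–79% |

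**Why the gap arises.** For two arms of n, the chi-square noncentrality is λ = n Σ (p₁ − p₂)²/(p₁ + p₂), summed over categories. With 17 equally likely levels in the placebo arm, n = 50 and 0.5 SD, λ = 5.79. Tested on 16 degrees of freedom (critical value 26.30), this gives 25% power by the asymptotic formula. The same λ on 1 degree of freedom (critical value 3.84) gives 67%, close to the rank-sum result. Almost all the signal is present; the chi-square dilutes it over 16 degrees of freedom. Sparse cells lower the simulated power further. With no true effect, the simulated chi-square rejects in 2.6–3.5% of trials instead of 5%.

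**Sample size equivalent.** By the same formula, chi-square on 17 equally likely levels needs about 167 per arm for 80% power at 0.5 SD. A two-sided comparison of means needs 63.

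**Three categories against the full scale.** At 0.5 SD and 50 per arm, moving from a chi-square on three categories to a rank test on all levels recovers 1 − 0.493/0.675 = 27% to 1 − 0.438/0.671 = 35% of the power of the better analysis.

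**The case against.** - **The plan does not commit to 17 levels.** This stands. A chi-square on the three first-step answers fits the text equally well. A reader might infer that the plan throws away most of the GSE's power, but that follows only if the full scale is tabulated. On three categories the loss is 15–19% of the power of a rank test on the same categories, and sparsity is not an issue.
- **The effect size is borrowed.** This stands. The documents give no GSE effect or distribution. The number rated at day 8 could also lie anywhere up to 80 per arm, since the 37% dropout is counted to day 15.
- **The measure carries little weight.** This stands. It is in none of the objectives, has no decision rule and has one placebo-controlled time point. Its stated purpose, estimating a minimal important difference, does not depend on the test between arms. A reader might infer that the efficacy conclusions are weakened, but fatigue, pain, anorexia and nausea have their own tests. Nor is the GSE the only patient-rated global measure, because the ESAS includes well-being.
- **Direction would be visible anyway.** This stands in part. The summaries by group would show it, but the test itself gives no directional evidence and no effect estimate.
- **Chi-square does test differences in distribution.** This is true, and it can detect patterns that a shift test misses, such as more patients at both extremes. The sparse table errs toward too few rejections, so no inflation of false positives should be inferred.

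**Conclusion.** The concern holds as a minor point. The GSE is ordered, the named test ignores the order, and under either reading of the categories an order-using test has more power against a shift. The gain is about 50 percentage points if all 17 levels are tabulated at 50 per arm, and about 10 points if three categories are used, assuming a normal latent shift of 0.5 SD and two-sided 0.05. The size therefore depends on a choice the plan leaves open, and leaving it open allows the categories to be picked after the data are seen. The practical consequence is confined to day 8: by days 22 and 29 both arms receive dexamethasone, so those comparisons do not set drug against placebo.

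**What to change.** In the GSE paragraph of Statistical Considerations:

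1. State the categories and their order, including where the lowest grades of better and worse sit relative to about the same.
2. Replace the chi-square with a Wilcoxon rank-sum test (tie-corrected) or a proportional-odds model on the full ordered scale.
3. Report a probability of superiority or a common odds ratio with its 95% confidence interval.
4. Name day 8 as the randomised drug-versus-placebo comparison and treat days 22 and 29 as descriptive.
5. Keep the table of categories by arm as description.

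The cost is two or three sentences, with no new data, visits or patients. The one trade-off is less sensitivity to differences that are not shifts, such as more patients at both extremes; the retained table lets a reader look for those.
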